12.1.2 Investigator

The term investigator refers to the trial PI or a formally delegated study physician.

12.2 Serious Adverse Events

During clinical investigations, AEs may occur which, if suspected to be IMP-related, might be significant enough to lead to important changes in the way the medicine is developed (e.g., change in dose, population, monitoring need, consent forms). This is particularly true for events that threaten life or function. Such SAEs will be reported promptly to regulatory authorities, applicable IRBs/IECs and investigators (expedited reporting) by GW.

An AE must only be classed as serious, i.e., a SAE, when the event falls into one of the following criteria:

- Results in death.
- Is life-threatening*.
- Requires inpatient hospitalization or prolongation of existing hospitalization.
- Results in persistent or significant disability/incapacity.

EudraCT Number: 2015-004904-50

Protocol V3 20Sep16

- Is a congenital anomaly/birth defect.
- Is medically significant **.

** Medical and scientific judgment should be exercised in deciding whether SAE reporting is appropriate in other situations. Important medical events may not be immediately life-threatening or result in death or hospitalization but may jeopardize the patient or may require intervention to prevent one of the other outcomes listed in the definition above. These should also usually be considered serious. Examples of such events are intensive treatment in an emergency room or at home for allergic bronchospasm, blood dyscrasias or convulsions that do not result in hospitalization, or development of drug dependency or drug abuse.

The sponsor considers all convulsive and non-convulsive status epilepticus events to be medically significant and should be reported to the Sponsor as medically significant SAEs

12.3 Reporting Procedures for Serious Adverse Events

All SAEs occurring during the trial must be reported to GW with any other supporting information and recorded in the AE section of the CRF. Any ongoing SAEs should be followed up until resolution wherever possible. For all deaths, the working diagnosis or cause of death as stated on a death certificate, available autopsy reports and relevant medical reports should be sent to GW promptly.

All SAEs must be reported directly to the GW Pharmacovigilance Department (PVD) within 24 hours of discovery or notification of the event. All SAE information must be recorded in the SAE report forms provided in the site files and faxed to the GW PVD (see APPENDIX 2). Additional information received for a case (follow-up or corrections to the original case) need to be detailed on a new SAE report form, signed/dated and faxed to the GW PVD and the AE section of the CRF must be updated.

Any other problem discovered after the safety follow-up visit which is deemed to be an unexpected safety issue and is likely to have an impact on patients who have taken part in the trial must be treated as an SAE and reported to the GW PVD. Such post-trial SAEs do not need to be recorded on the patient's CRF if editing rights to the CRF have been removed due to final trial data lock. GW PVD may request safety

^{*} The term "life-threatening" in the definition of "serious" refers to an event in which the patient was at risk of death at the time of the event; it does not refer to an event which, hypothetically, might have caused death if it were more severe.

EudraCT Number: 2015-004904-50

Protocol V3 20Sep16

follow-up information after the final trial visit in order to investigate a potential safety issue.

Contact details for the GW PVD are provided at the front of the site files for all trial sites, and upon the GW SAE report form.

12.4 Causality Assessment

Causality assessment is required for all AEs and SAEs. Causality assessment must only be assigned by the investigator. All cases judged as having a reasonable suspected causal relationship to the IMP must be reported as such. The expression "reasonable causal relationship" is meant to convey in general that there are facts (evidence) or arguments to suggest a causal relationship.

The following question which must be answered by the investigator for all AEs is used to capture the reasonable causal relationship of an event to the IMP:

"In your opinion is there a plausible relationship to the IMP?" The answer is either "yes" or "no".

Events that start before the first dose of IMP (pre-treatment) should be considered as not causally related. Where a pre-treatment event worsens in severity following the first dose of IMP, a new event record should be entered into the CRF.

Considering the explanation given above, investigators are strongly encouraged to express their opinion on what the cause of an AE might be. For individual patients, the investigator is usually in the best position to assess the underlying suspected cause of an AE. For all AEs and especially SAEs, it is important that the investigator assess not only the possible role of the IMP but also other potential contributing factors. Factors for consideration of the underlying cause may include:

- Medical and disease history.
- Lack of efficacy/worsening of treated condition.
- Concomitant or previous treatment.
- Withdrawal of IMP.
- Protocol-related procedure.

12.5 Reporting Procedures for All Adverse Events

All AEs (including SAEs) occurring during the trial will be reported on the running logs in the AE section of the CRF. This includes all events from the time following

EudraCT Number: 2015-004904-50

Protocol V3 20Sep16

screening (Visit 1) up to and including the post-treatment follow-up visit, whether or not attributed to IMP and observed by the investigator or patient.

The following information will need to be provided for all AEs:

A) Adverse Event (Diagnosis or Syndrome if Known, or Signs and Symptoms)

Where the investigator cannot determine a diagnosis, signs or symptoms should be recorded in the AE section of the CRF. Once a diagnosis has been determined the AE section of CRF must be updated to reflect the diagnosis in replacement of the original symptoms. In circumstances where only a provisional diagnosis is possible (working diagnosis), the CRF must be updated to reflect the provisional diagnosis in replacement of the original symptoms. In some circumstances it may be relevant for the investigator to include the symptoms alongside the diagnosis in the verbatim event description. However, the diagnosis (full or provisional) should be clearly stated, e.g., fever and malaise due to a respiratory tract infection.

B) Adverse Event Start Date and Stop Date

The start and stop dates of the event must be provided. All AEs require these fields to be completed in full. Partial dates or missing dates are not normally acceptable and significant effort must be undertaken to obtain any unknown information. If a precise date is not known an estimated date should be provided instead. When a complete date cannot be given, record as much information as possible (i.e., month and year or, in exceptional circumstances, just year). When the actual start date becomes known the CRF must be updated to replace the previously recorded date.

C) Outcome

The outcome of the event must be recorded accurately and classified into one for the following categories:

- Recovered.
- Recovered with sequelae.
- Continuing.
- Patient died.

D) Severity

When describing the severity of an AE the terms mild, moderate, or severe should be used. Clinical judgment should be used when determining which severity applies to any AE.

EudraCT Number: 2015-004904-50

Protocol V3 20Sep16

If the severity of an AE fluctuates day-to-day, e.g., a headache or constipation, the change in severity should not be recorded each time; instead, only the worst observed severity should be recorded with AE start and stop dates relating to the overall event duration, regardless of severity.

A severe AE is not the same as a SAE. For example, a patient may have severe vomiting but the event does not result in any of the SAE criteria above. Therefore, it should not be classed as serious.

E) Causality

See Section 12.4 above.

F) Action Taken with Trial Medication

This question refers to the action taken with the IMP due to an AE. The action with the IMP must be classed as:

- None.
- Dose reduced temporarily.
- Dose reduced.
- Trial medication interrupted.
- Trial medication stopped.

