International normalized ratio	A calculation made to standardize prothrombin time.
Investigational medicinal product	Term used to describe both investigational active product and reference therapy (placebo).
Investigator	Trial principal investigator or a formally delegated study physician.
Status epilepticus	Any seizure lasting 30 minutes or longer.

EudraCT Number: 2015-004904-50

Protocol V3 20Sep16

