Patients from the pivotal phase who enter the OLE will taper their blinded IMP while simultaneously titrating their OLE IMP (GWP42003-P) over 4 days according to the titration regimen, an example titration regimen up to 40 mg/kg/day over 4 days is shown in Table 8.1.2-2. No further titration will be required for patients in the pilot phase; they will remain on the same GWP42003-P dose going into the OLE phase. Daily safety checks will be made during the first week of OLE IMP dosing. GWP42003-P may be discontinued at any time during the OLE phase, at the discretion of the investigator (see Section 9.1.2).

Table 8.1.2-2 Example Titration Regimen: Transition to the OLE Phase (Pivotal Phase Only)						
Day	Blinded IMP Dosage ¹	OLE IMP Dosage ¹	Total Daily IMP Dose (Patients Randomized to Placebo) ²	Total Daily IMP Dose (Patients Randomized to GWP42003-P) ²		
15	20 mg/kg (am/pm)	0	0	40 mg/kg		
16	15 mg/kg (am/pm)	5 mg/kg (am/pm)	10 mg/kg	40 mg/kg		
17	10 mg/kg (am/pm)	10 mg/kg (am/pm)	20 mg/kg	40 mg/kg		
18	5 mg/kg (am/pm)	15 mg/kg (am/pm)	30 mg/kg	40 mg/kg		
19 onwards	0	20 mg/kg (am/pm)	40 mg/kg	40 mg/kg		

Volumes of IMP to be taken each day will be calculated using the patient's weight and the required dose.

²Patients may taper to and remain on a lower dose if unable to tolerate the target dose.

²Patients may taper to and remain on a lower dose if unable to tolerate the target dose.

EudraCT Number: 2015-004904-50

Protocol V3 20Sep16

Following the end of treatment, all patients will commence a taper period (tapering 10% per day for 10 days). Patients who withdraw early should also begin the taper period following the withdrawal visit (unless continued dosing is not possible due to an AE). Patients who discontinue IMP during the OLE phase should also begin the taper period following the investigator's decision to discontinue. The IVRS/IWRS will generate the patient's daily IMP dosing volumes for the 10-day taper period.

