13.3 Analysis Sets

Statistical analysis will be performed according to a statistical analysis plan (SAP). Details of any deviations from the SAP will be documented in the clinical study report.

EudraCT Number: 2015-004904-50

Protocol V3 20Sep16

There will be 3 analysis sets for this trial:

Pilot or Pivotal Phase Safety

All patients exposed to at least 1 dose of IMP during the pilot or pivotal phase will be used for summaries of the safety endpoints during both phases.

OLE Phase Safety

All patients exposed to at least 1 dose of IMP during the OLE phase will be used for summaries of the safety endpoints during the OLE phase.

Intention to Treat (ITT)

All patients in the pivotal phase who are randomized and receive IMP will be included and analyzed according to their randomized treatment group. The ITT analysis set is the primary analysis set for all efficacy endpoints.

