13.6.5.2 Adverse Events

AEs will be coded according to the Medical Dictionary for Regulatory Activities dictionary.

A TEAE is one that started, or worsened in severity or seriousness, following the first dose of IMP.

Descriptive presentations of TEAEs will be given by preferred term and system organ class for the safety analysis set for each phase of the trial separately. The number of patients reporting at least 1 TEAE will be provided.

The following summaries will be produced:

EudraCT Number: 2015-004904-50

Protocol V3 20Sep16

- All-causality TEAEs.
- Treatment-related TEAEs.
- All-causality TEAEs by severity.
- All-causality TEAEs by sex.
- All-causality serious TEAEs.
- Treatment-related serious TEAEs.
- TEAEs reported as leading to permanent cessation of study treatment.
- Treatment-related TEAEs reported as leading to permanent cessation of study treatment.
- Fatal TEAEs.

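### A fluctuating AE that peaks after the first open-label dose carries that severity into the earlier phase's table, because no rule opens a new AE record at that dose

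*Protocol*

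**What the plan says.** Four places in the plan bear on this.

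- **Recording of severity (Protocol 12.5).** The rule opens with its scope: "If the severity of an AE fluctuates day-to-day, e.g., a headache or constipation". For such an event the changes are not entered one by one; instead "only the worst observed severity should be recorded with AE start and stop dates relating to the overall event duration, regardless of severity".
- **New records (Protocol 12.4).** "Where a pre-treatment event worsens in severity following the first dose of IMP, a new event record should be entered into the CRF". This is the only rule that opens a second record for a continuing event. The Definition of Terms makes IMP cover placebo as well as active product.
- **Analysis (Protocol 13.6.5.2; SAP 4.8.2).** "A TEAE is one that started, or worsened in severity or seriousness, following the first dose of IMP". The SAP keeps this definition. The protocol presents TEAEs, including by severity, "for the safety analysis set for each phase of the trial separately". The SAP plans Table 11.4.1 for severity in the pilot phase and Table 11.4.2 for the OLE, and counts each subject once at the most intense occurrence.
- **The switch (Protocol 8.1.2).** "Patients from the pivotal phase who enter the OLE will taper their blinded IMP while simultaneously titrating their OLE IMP (GWP42003-P) over 4 days". In the example regimen the first open-label dose is on Day 16. Pilot infants stay on the same GWP42003-P dose.

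The OLE safety set in Protocol 13.3 says which patients count, not which events: "All patients exposed to at least 1 dose of IMP during the OLE phase will be used for summaries of the safety endpoints".

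**The concern.** The TEAE definition counts worsening as well as onset. Applying it at a given dose requires knowing the severity before and after that dose. Section 12.5 removes this information for a fluctuating event, and section 12.4 restores it only around the first dose of IMP. A placebo infant's first dose of IMP is placebo on Day 1, so the new-record rule gives nothing at the first dose of active drug.

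At stake is the meaning of a severity table headed with one phase. In the planned pivotal phase, the placebo column could contain a severity that the infant reached only on open-label GWP42003-P. In the pilot phase, where safety is a primary endpoint, the pilot column could contain a severity first reached during the OLE.

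**Working it through.** The plan gives no figure to reproduce here, so the check is a trace of one case through the rules.

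**Case (hypothetical).** A placebo infant has an AE that starts before Day 15, is at most mild during the blinded phase, varies from day to day, continues past Visit 4, and is severe on some days after open-label dosing begins.

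1. *Does 12.5 apply?* Yes, because the severity fluctuates. There is one record, its start date is in the blinded phase, and its severity is severe.
2. *Does 12.4 open a second record?* No. The event began after the first dose of IMP (placebo), so it is not a pre-treatment event.
3. *Is the date of the peak kept on the AE record?* The items that 12.5 requires for each AE are the term, start and stop dates, outcome, severity, causality and action taken with the medication. A date for the worst severity is not among them.
4. *Where does the record appear?* Neither document says how an event that spans two phases is assigned, so each possible rule has to be tried:

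| Assignment rule | Pivotal (placebo) table | OLE table |
|---|---|---|
| By start date | Severe | Not shown |
| By any overlap with the phase | Severe | Severe |
| By date of worst severity | Would not show severe | Severe |
| What happened in the case | Mild | Severe, worsened |

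The third rule cannot be applied from the AE record, because step 3 shows that the date it needs is not required. Under either of the first two rules, the pivotal table shows a severity that was not reached in that phase. Whether the OLE table shows the event depends on the missing rule. The nearest timing rule is SAP 4.2.8.1, which imputes a missing onset date to decide whether an event falls in the treatment period; it does not deal with phases.

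**Same case in a pilot infant.** Steps 1 to 4 run identically, with Table 11.4.1 in place of the pivotal table and Table 11.4.2 for the OLE. The infant is on GWP42003-P throughout.

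**Sustained worsening.** If the event steps up and stays up after the switch, 12.5 does not cover it and 12.4 does not require a new record. A second record is neither required nor forbidden, so sites may differ.

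**How many could be affected.**
- Planned placebo infants: 192 / 3 = 64. This is a ceiling, since not all will enter the OLE with an ongoing fluctuating AE.
- Planned infants on the two active arms, under the same rule: 2 × 64 = 128.
- Pilot infants in SAP 4.1: 9.
- Weight of one misplaced record: 1/64 = 1.6% of the placebo arm; 1/9 = 11.1% of the pilot infants.

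The documents give no rate for AEs that are ongoing at Day 15, fluctuate and peak later, so the number of affected infants cannot be estimated.

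**The case against.** Several stronger readings are tempting, and the documents do not support them.

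- *Any AE that worsens after the switch is booked to placebo.* Section 12.5 is limited to day-to-day fluctuation. For sustained worsening there is a gap, not a rule that gives the wrong answer.
- *The OLE table misses these events.* That needs assignment by start date, which neither document states. Under assignment by overlap the OLE table shows them.
- *The error makes the drug look safer.* The 128 planned active-arm infants may also enter the OLE under the same rule, and their pivotal records would also take on severity reached later. The net direction is unproven. For pilot infants the effect is to make the pilot phase look worse.
- *The reported analysis misplaces events between placebo and active drug.* SAP sections 2.2 and 5 confine the analysis to single-arm, open-label phases in pilot patients. No placebo data are analysed.

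It can also be said that worsening at the switch would not go unseen. Caregivers keep a daily diary, AEs are asked about daily from Day 16 to Day 22 and again at Visit 5, an event that becomes serious is reported within 24 hours, and the SAP lists every AE by cohort and subject. This stands as mitigation. It does not put a dated severity on the AE record from which the severity tables are built.

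One might add that Protocol 13.2 anticipates locking the pivotal database before the OLE ends. That limits the effect only for worsening after the lock. Each infant's switch starts right after Visit 4, so most would probably have passed it by then, with the AE running logs updated.

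**Conclusion.** The point holds in a limited form. For an AE that fluctuates day to day, the stated recording rules put severity reached after the first OLE dose into the earlier phase's severity table, whether records are assigned by start date or by overlap. This conflicts with separate reporting by phase and with a TEAE definition that counts worsening. It is a stated rule that gives a wrong result, not merely missing detail.

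Under the protocol as planned, at most 64 placebo infants could have severity from active drug shown under placebo; the actual number and the net direction of bias are unknown. Under the SAP the issue is smaller: pilot versus OLE in 9 infants, all on GWP42003-P, where one record moves the pilot severity table by 1/9. It is worth correcting because the remedy is cheap and extends logic that the protocol already uses at the first dose.

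**What to change.** In Protocol 12.4 and 12.5, and in the CRF completion guideline, add a sentence to this effect:

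> An AE that is ongoing at the first OLE dose and worsens in severity or seriousness after that dose is entered as a new record with its own start date. The earlier record keeps the worst severity seen before that dose.

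This covers fluctuating and sustained worsening alike. In SAP 4.8.2, state that AE records are assigned to phase by start date, with the new record's own start date used for the later phase.

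The cost is a few more AE records, and some events will be counted once in each phase, which a table footnote should say. The SAP change alone cannot recover severity before the first OLE dose for records already collected under the present rule. If any such records exist among the 9 pilot infants, a footnote to Table 11.4.1 should say that the severity shown may have been reached in the OLE.

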12.6 Follow-up Procedures for Adverse Events

The investigator may be asked to provide follow-up information to the GW PVD for any AEs reported or during the investigation of potential safety issues. Such requests for additional safety information may occur after the safety follow-up visit (i.e., after the trial).

AEs considered related to the IMP by the investigator or the sponsor should be followed up until resolution or the event is considered stable.

It will be left to the investigator's clinical judgment whether or not an AE is of sufficient severity to require the patient's removal from treatment. A patient's parent(s)/legal representative may also voluntarily withdraw the patient from treatment due to what he or she perceives as an intolerable AE. Further details of withdrawal are presented in Section 10. If either of these occurs, the patient must undergo an end of treatment assessment and be given appropriate care under medical supervision until symptoms cease or the condition becomes stable. If a safety concern is identified following withdrawal of a patient, GW may contact the investigator for additional follow-up information.

EudraCT Number: 2015-004904-50

Protocol V3 20Sep16

12.7 Potential Cases of Drug-Induced Liver Injury

All investigational sites are required to submit to the GW PVD the laboratory results for any patient after starting treatment that meets the criteria for the selected laboratory parameters as follows:

- ALT or AST > 3 × ULN with the appearance of fatigue, nausea, vomiting, right upper quadrant pain or tenderness, fever, rash, and/or eosinophilia (> 5%).
- ALT or AST $> 8 \times ULN$.
- ALT or AST $> 5 \times$ ULN for more than 2 weeks.
- ALT or AST $> 3 \times$ ULN and (TBL $> 2 \times$ ULN or INR > 1.5).

These reports must be sent to the GW PVD using the fax number for SAE reporting (see APPENDIX 2) within 24 hours of becoming aware of the results. In addition, please send a copy of the patient's baseline laboratory results with all reports to the GW PVD.

Abnormal values in AST and/or ALT concurrent with abnormal elevations in TBL that meet the criteria outlined above are considered potential cases of drug-induced liver injury and will be considered as protocol-defined criteria for withdrawal and important medical events. The investigator will arrange for the patient to return to the investigational site as soon as possible (within 24 to 48 hours of notice of abnormal results) for repeat assessment of ALT, AST, TBL, alkaline phosphatase and gamma-glutamyl transferase levels, detailed history and physical examination. Patients should be followed in this way until all abnormalities have normalized (in the investigator's opinion) or returned to the baseline state, however, if the above transaminase elevation criteria are confirmed by the first set of follow-up laboratory tests, the patient must be withdrawn from the trial.

Elevations in ALT or AST $> 3 \times \text{ULN}$ or TBL $> 2 \times \text{ULN}$ alone are not considered potential cases of drug-induced liver injury, but will be followed as detailed above, within 72 hours' notice of abnormal results.

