10 WITHDRAWAL

In accordance with the Declaration of Helsinki⁵⁶, the International Conference on Harmonisation (ICH) Tripartite Guideline for GCP Topic E6(R1)⁵⁷, the FDA regulations relating to GCP and clinical trials^{58,59,60}, the EU Clinical Trials Directive⁶¹, the EU GCP Directive⁶² and/or other applicable regulations, a patient has the right to withdraw from the trial at any time and for any reason, with no obligation to provide a reason, and without prejudice to his or her future medical care by the physician or at the institution.

The patient must be withdrawn from the trial if any of the following apply:

- Any issue with eligibility criteria that is considered to potentially compromise the safety of the patient.
- Administrative decision by the investigator, GW, or a regulatory authority.
- Protocol deviation that is considered to compromise potentially the safety of the patient.
- Withdrawal of the patient's parent(s)/legal representative consent.
- QTcB of 500 msec or greater on ECG, or a shift from baseline QTcB of 60 msec or greater.

Note: Prior to withdrawal for the QTcB shifts noted above, the investigator should repeat the ECG three times and contact the GW medical monitor. If the above QTcB criteria are confirmed, the patient must be withdrawn from the trial.

- Lost to follow-up.
- ALT or AST > 3 × ULN with the appearance of fatigue, nausea, vomiting, right upper quadrant pain or tenderness, fever, rash, and/or eosinophilia (> 5%).
- ALT or AST $> 8 \times ULN$.
- ALT or AST $> 5 \times ULN$ for more than 2 weeks.
- ALT or AST $> 3 \times$ ULN and (TBL $> 2 \times$ ULN or INR > 1.5).

Note: Prior to withdrawal for the transaminase elevations noted above, the Investigator may choose to confirm the transaminase elevations by repeating the following laboratory tests within 24 to 48 hours: ALT, AST, TBL, INR, % eosinophils, gamma glutamyl transferase and alkaline phosphatase. **Should the above**

EudraCT Number: 2015-004904-50

Protocol V3 20Sep16

transaminase elevation criteria be confirmed, the patient must be withdrawn from the trial.

Patients may also be withdrawn from the trial for any of the following:

- Any other issue with eligibility criteria (non-safety related).
- Any requirement to increase the dose of concomitant AED(s) or to add in new AED(s) during the pilot or pivotal phase.

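### Protocol Section 12.7 does not agree with its own four liver criteria or with Section 10 on which elevations count as potential liver injury, when they are retested, and whether a repeat must precede withdrawal

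*Protocol*

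**What the plan says.** Protocol Section 10 states: "The patient must be withdrawn from the trial if any of the following apply". Four liver criteria follow:

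- ALT/AST above 3 × ULN with symptoms or eosinophilia;
- ALT/AST above 8 × ULN;
- ALT/AST above 5 × ULN for more than two weeks;
- ALT/AST above 3 × ULN with TBL above 2 × ULN or INR above 1.5.

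A note adds that, before withdrawal, "the Investigator may choose to confirm the transaminase elevations by repeating the following laboratory tests within 24 to 48 hours". It ends by saying that, should the "transaminase elevation criteria be confirmed, the patient must be withdrawn from the trial". The synopsis carries the same list and note. SAP 2.3 copies the list without the note.

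Section 12.7 repeats the four criteria and requires sites to send the results to pharmacovigilance "within 24 hours of becoming aware of the results". It then defines potential drug-induced liver injury: "Abnormal values in AST and/or ALT concurrent with abnormal elevations in TBL that meet the criteria outlined above are considered potential cases". The same sentence makes those cases withdrawal criteria and important medical events. The infant is to be brought back for repeat tests within 24 to 48 hours of notice, and must be withdrawn if the first follow-up tests confirm the transaminase criteria. The closing sentence deals with ALT/AST above 3 × ULN, or TBL above 2 × ULN, on its own: these "alone are not considered potential cases of drug-induced liver injury, but will be followed as detailed above, within 72 hours' notice of abnormal results".

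**The concern.** A reader moving from the list in Section 12.7 to the paragraph beneath it finds that the classification covers only part of the list. A result can meet a listed criterion, be reportable within 24 hours and be a withdrawal criterion in Section 10, yet fall outside the sentence that makes it a potential liver-injury case and an important medical event. The closing sentence then appears to place some of the same results on a longer follow-up clock.

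Safety is a primary endpoint of the pilot and OLE (Protocol 4.1.1.1 and 4.1.1.3; SAP 2.5). Important medical events are usually to be treated as serious (Protocol 12.2), so the label feeds the tables of serious treatment-emergent events. Whether a repeat is needed first affects which infants are withdrawn, and so the tables of events leading to discontinuation. About 50 sites are expected to apply these rules (Protocol 4.2) using local laboratories (Protocol 9.2.10). Protocol 8.2 itself describes the risk of valproate hepatotoxicity as high in this population.

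**Working it through.** The documents give no figure to reproduce. The check is a comparison of the rules, criterion by criterion. "concurrent with abnormal elevations in TBL that meet the criteria outlined above are considered potential cases of drug-induced liver injury" is the sentence tested in the fourth column; the closing sentence of Section 12.7 is tested in the fifth.

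| Result | Section 10 | 12.7 list (24-hour report) | 12.7 TBL sentence (potential liver injury, important medical event) | 12.7 closing sentence (72 hours) |
|---|---|---|---|---|
| > 3 × ULN with symptoms or eosinophilia | Withdrawal criterion | Listed | Not covered unless TBL is also raised | Not reached: the elevation is accompanied |
| > 8 × ULN, isolated | Withdrawal criterion | Listed | Not covered | Reached on its wording |
| > 5 × ULN for more than 2 weeks, isolated | Withdrawal criterion | Listed | Not covered | Reached on its wording |
| > 3 × ULN and TBL > 2 × ULN | Withdrawal criterion | Listed | Covered | Not reached |
| > 3 × ULN and INR > 1.5, TBL normal | Withdrawal criterion | Listed | Not covered | Not reached: INR is raised too |

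**Classification.** The TBL sentence fully covers one branch of one criterion. Three of the four criteria, and the INR branch of the fourth, can be met without it. This mismatch lies between Section 12.7 and its own list, and between Section 12.7 and Section 10.

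**Closing sentence.** It starts at 3 × ULN and has no upper bound or exception. Two of the four criteria (> 8 × ULN, and > 5 × ULN for more than two weeks) can be met by a transaminase elevation alone, so they fall within its wording while also being listed.

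**Retest window.** Section 10 gives 24 to 48 hours, and so does the repeat visit in Section 12.7. The closing sentence gives 72 hours. For the two isolated criteria the outer limit is 48 or 72 hours depending on the reading: 72 − 48 = 24 hours.

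**Repeat before withdrawal.** In Section 10 the investigator may choose to repeat. If no repeat is done, the mandatory list applies to a single value. In Section 12.7 a repeat is required on either reading, because the closing sentence sends isolated elevations to the same follow-up, only later.

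**Withdrawal after confirmation.** Both sections require it for a listed criterion. Here they agree.

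**Scale in the summaries.** SAP 4.1 gives 9 pilot patients. One infant classified differently moves a pilot percentage by 1/9 = 11.1 points (1/10 = 10 points on the protocol's planned 10). This shows sensitivity if such a case occurs; nothing in the documents says that one did.

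**The case against.** The strongest defence is that a coherent reading exists. The closing sentence names the two components of the combined ALT/AST-plus-TBL criterion, so it can be taken to mean one component by itself with no listed criterion met. On that reading a value above 8 × ULN is governed by the list, is reported within 24 hours, and leads to withdrawal once confirmed. The sections then do not collide. This reading is reasonable, but the protocol does not state it, and it does not repair the TBL sentence or the optional-versus-required repeat.

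A reader might infer something stronger: that the two sections are flatly incompatible on withdrawal for an isolated value above 8 × ULN. The documents do not support that, since Section 12.7 lists the value and requires withdrawal on confirmation. A reader might also infer that seriousness depends on which section a site follows. Section 10 says nothing about seriousness; that ambiguity sits inside Section 12.7.

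Two further limits stand. SAP 4.8.3 tabulates ALT/AST above 3 × ULN and TBL above 2 × ULN from the laboratory values, so those counts do not depend on how a site reads the text; they also do not separate values above 8 × ULN. And although Protocol 13.6.2.2 scores pivotal-phase withdrawals as non-responders, SAP Section 5 omits the pivotal phase, so no effect on the planned efficacy analyses can be claimed through that route.

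**Conclusion.** The point holds as an internal inconsistency in stated safety rules. The TBL sentence omits three of four listed criteria and the INR branch of the fourth. For two criteria met in isolation, both the classification and the retest window (outer limits 24 hours apart) are unclear. The repeat before withdrawal is optional in one section and required in the other. The sections agree on withdrawal after confirmation.

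The consequence is limited to when infants are retested and to serious-event and withdrawal reporting in the pilot and OLE safety summaries. The conclusion rests on reading the sentences as written. The effect on any count also assumes that a qualifying elevation occurs and that sites read the text differently.

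**What to change.** Reconcile Section 10, Section 12.7 and the matching synopsis note. For each of the four criteria, state once and in identical terms:

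- the repeat-test window;
- whether a repeat is required before withdrawal;
- whether the result is a potential liver-injury case and an important medical event.

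State explicitly how the closing sentence of Section 12.7 relates to the listed criteria. The copy of the list in SAP 2.3 should then match. Which clinical rule applies is for the sponsor's medical team, and this review takes no position on it.

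The cost is wording in two protocol sections and the synopsis note, plus the SAP copy. Reconciling the text does not in itself call for new tests, visits or analyses.
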